## **Other Comparisons and Outcomes**

1. Baseline characteristics - Comparison of the rates of specific characteristics between both treatment groups I and II using a one-tailed Fischer's exact test and/or unpaired t test.
2. Use of epinephrine - Comparison of the rates of epinephrine rescue medication use between both treatment groups I and II using a one-tailed Fischer's exact test.
3. Mini-RQLQ - Kaplan-Meier or similar repeated measures test will also be used to calculate the effect of treatment over time between both groups I and II.
4. Drop out - Comparison of the drop out rates between both groups I and II using a one-tailed Fischer's exact test.
5. Trend tests - For these study data, representing a continuous response, an appropriate test, such as the Jonckheere-Terptsra trend test, based on a sum of Mann-Whitney-Wilcoxon tests may be sensitive and reveal a mild trend where pair-wise comparisons may not be able to find significant differences and not be as helpful. Other trend tests may also be used.

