#### **12.1.3 Efficacy Analysis**

The intent-to-treat approach will be used. Baseline characteristics will be described using mean and standard deviation for continuous variables and medians and ranges for discrete variables. The primary efficacy variable of comparing PMA versus placebo will be undertaken by quantifying the instrument-assessment scores of each study subject in each of the two therapeutic arms of the investigation. The p-value, least square (LS) treatment means, difference between the LS treatment means, and 95% confidence intervals for the treatment differences will be presented. The success of blinding will be assessed by asking the patient and staff which treatment set they thought they were getting, i.e. active treatment or placebo. The results will be recorded at each study visit.

Total Nasal Symptoms Score (TNSS) and the Mini-RQLQ attached in Appendix F will be used to evaluate clinical efficacy. TNSS along with rescue medication use is recorded at home on a daily

card as shown in Appendix K. Daily scores will only be recorded on weeks 2, 10, and 14. The mini-RQLQ will be recorded in person at screening, during each study visit, and at followup. The correct use of the TNSS survey is to score 0-12 based on symptoms reported that day while the mini-RQLQ is scored 0-84 based on symptoms reported over the past week. Higher scores indicate worse symptoms.

The primary outcome measure is the average daily combined score (DCS) which is calculated by adding the average TNSS + average medication score as well as the mini-RQLQ at weeks 2,10 and 14.

Secondary outcomes will include the adverse events rate and TNSS between both groups using a one-tailed Fischer's exact test and/or unpaired t test.

Other outcomes include baseline characteristics, use of epinephrine, and drop out between both treatment groups I and II using a one-tailed Fischer's exact test and/or unpaired t test. Trend tests for comparison of both groups will be performed such as the Jonckheere-Terptsra trend test. A sum of Mann-Whitney-Wilcoxon tests may also be sensitive and reveal a mild trend. Other trend tests may also be used.

A Kaplan-Meier or similar product limit estimator function will also be used to calculate the effect of treatment over time.

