## STUDY DESIGN AND METHODS

### Study Design

This is a phase 2 proof of concept study. It is being undertaken to characterize and quantify the clinical difference in signs and symptoms that may evolve when subjects with active seasonal or perennial allergic rhinitis (SAR/PAR) are administered a sub-cutaneous form of immunotherapy in a double-blind, prospective, controlled six weeks study wherein a proprietary mixture of FDA approved allergens (PMA) is compared with saline placebo.

Randomization to active PMA versus placebo treatment is on a 1 to 1 ratio. A double-blind study design is used to minimize outcome bias. Randomization measures to minimize bias at study entry include computerized random assignment of treatment versus placebo vials.

Subjects who are receiving nasal steroids for their SAR/PAR at screening may continue in the screening process if they agree to discontinue their therapy and commence a 14-day wash-out period of their medication prior to receiving active/placebo immunotherapy. Potential study subjects who, at screening, are not on active treatment for their SAR/PAR and asthma may enter directly into the investigation provided they fulfil entry and exclusion criteria and screening testing requirements.

The population to be studied consists of male and female adults aged 18 years to 65 years who are actively manifesting SAR/PAR have a score of at least 28 on the mini-RQLQ and 6 on the TNSS scale.

[figure not shown]
The active treatment phase of the study will be for six weeks with a safety follow-up assessment at 30 days post-treatment. No interim analysis is planned.

The study immunotherapy that will be evaluated in this study is a new innovative proprietary mixture of FDA approved allergens which has been clinically developed and evaluated, during the past three decades, in some 20,000 patients by the inventor of the mixture (see 3.2). In clinical evaluation this patented antigen mixture has provided clinical symptomatic relief to patients with SAR/PAR in as brief a period as three administrations of immunotherapy injections and has an observed overall success rate of approximately 80 to 90 percent of such treated subjects.

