### Primary Outcomes

1. Daily Combined Score (DCS) – Comparison of the delta visit 2 to visit 17 (change in score) between both treatment groups I and II using an unpaired t test.
2. Daily Combined Score (DCS) – Comparison of the delta visit 2 to visit 18 (change in score) between both treatment groups I and II using an unpaired t test.
3. mini-rhinoconjunctivitis quality of life questionnaire (RQLQ) - Comparison of the delta visit 2 to visit 17 (change in score) between both treatment groups I and II using an unpaired t test.
4. mini-RQLQ - Comparison of the delta visit 2 to visit 18 (change in score) between both treatment groups I and II using an unpaired t test.

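### Kaplan-Meier is named for the repeated mini-RQLQ score with no event defined, and SAP and protocol offer different families of method, so a supportive analysis is left open

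*Combined protocol and SAP*

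**What the plan says.** SAP, Other Comparisons and Outcomes, item 3, plans this for the mini-RQLQ: "Kaplan-Meier or similar repeated measures test will also be used to calculate the effect of treatment over time". Protocol section 12.1.3 has a matching sentence: "A Kaplan-Meier or similar product limit estimator function will also be used to calculate the effect of treatment over time". The protocol sentence names no endpoint; the SAP ties the analysis to the mini-RQLQ. The SAP also states that it follows protocol sections 12.1 to 12.3.

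On the variable itself, section 12.1.3 says that "the mini-RQLQ is scored 0-84 based on symptoms reported over the past week" and that "The mini-RQLQ will be recorded in person at screening, during each study visit, and at followup". Appendix A of the protocol places the survey at visit 1, visits 2 to 17 and visit 18.

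Elsewhere the SAP treats the data as continuous. Item 5 of the same list begins "For these study data, representing a continuous response, an appropriate test, such as the Jonckheere-Terptsra trend test". Items 3 and 4 under Primary Outcomes compare mean change, the latter as "mini-RQLQ - Comparison of the delta visit 2 to visit 18 (change in score) between both treatment groups I and II using an unpaired t test".

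**The concern.** Kaplan-Meier estimates the distribution of time until an event. It needs a subject to pass from one state to another at a known or bounded time. A questionnaire total that can fall and rise again from visit to visit supplies no such time until someone defines the event: a threshold, an absolute or percentage fall, first occurrence or sustained. Nothing of that kind is written.

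The two documents also disagree about the fallback. In the SAP it is a repeated-measures test, in the protocol another product-limit estimator. These are different families answering different questions: a difference in mean score over time, or a difference in time to response.

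At stake is the credibility of one supportive result. Whoever runs it must choose the family of method, and then the event or the model. If those choices are made with treatment codes known, the p-value and confidence interval lose their usual meaning.

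**Working it through.** **1. What each method needs, and what the documents give**

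| Needed | Found in the documents |
|---|---|
| Event on the mini-RQLQ | None. The only cut-off is for eligibility: subjects must "have a score of at least 28 on the mini-RQLQ and 6 on the TNSS scale" |
| Time origin | None stated for this analysis (visit 2 is the reference for the t tests) |
| Censoring rule | None |
| Test between arms | None; log-rank is not mentioned |
| Repeated-measures model, covariance, covariates, contrast | None |
| Missing-data assumption | None |

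**2. Could the sample-size assumption supply the event?** Protocol section 12.3 assumes efficacy of 80% against 30%, two-sided alpha 0.05 (section 12.1.1) and 80% power, and states 28 subjects. The usual two-proportion formula with pooled variance under the null gives

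n per arm = [1.960 × √(2 × 0.55 × 0.45) + 0.842 × √(0.8 × 0.2 + 0.3 × 0.7)]² / 0.5² = (1.379 + 0.512)² / 0.25 = 14.3, so 15 per arm and 30 in total.

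That is within two subjects of the stated 28; 14 per arm gives 79.1% power. So the calculation treats efficacy as a yes/no outcome, but no document says what counts as yes. It cannot fill the gap.

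**3. Structure of the data.** The score has 14 items of 0 to 6, hence 14 × 6 = 84. With visit 2 as baseline, visits 3 to 18 give 16 later scores per subject. The recall period is a week and treatment visits are twice weekly, so neighbouring scores cover overlapping days.

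**4. Does the missing event matter?** The documents give no variance or trajectory for the mini-RQLQ, so this is an illustration on assumed inputs:
- 18 per arm, no dropout, 16 equally spaced later visits.
- Baseline mean about 42 (SD 10, floor 28), taken as free of visit noise.
- Mean fall growing linearly to 20 points on active and 8 on placebo at the last visit.
- Between-subject SD of that fall 14; visit-to-visit SD 7 or 4.
- 600 simulated trials per setting (Monte Carlo standard error at most √(0.25/600) = 0.02).

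Share of log-rank tests with p < 0.05:

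| Event | Visit SD 7 | Visit SD 4 |
|---|---|---|
| Fall of 30% or more | 0.35 | 0.55 |
| Fall of 50% or more | 0.44 | 0.47 |
| Score below 28 | 0.18 | 0.26 |
| Fall of 10 points or more | 0.30 | 0.56 |
| Fall of 30% or more at two consecutive visits | 0.50 | 0.54 |

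With the data-generating scenario held fixed, the choice of event alone moves the result from 0.18 to 0.50 in one column and from 0.26 to 0.56 in the other. The figures themselves belong to the assumptions; the dependence on an unstated choice is the point.

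**5. What a replacement model can carry.** An unstructured covariance over 16 visits has 16 × 17 / 2 = 136 parameters. With about 36 subjects that cannot be estimated reliably. A random intercept plus AR(1) has three: intercept variance, residual variance and one correlation.

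**The case against.** The best defence has four parts.

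- **The SAP sentence allows a repeated-measures test.** True. A reader might infer that the analysis cannot be done at all; that holds only for the Kaplan-Meier option. The permission does not settle the matter, because no model is named and the protocol section that the SAP follows gives a product-limit estimator as the alternative.
- **Other analyses could use the visit scores.** Also true. The SAP lists a symptom-score trend analysis as a secondary endpoint, and item 5 allows trend tests without naming a variable. A reader might infer that item 3 is the only route to the visit-level data, or that this information is lost. Neither is supported: the scores are collected whatever happens to item 3.
- **There are blinded routes to repair.** Protocol section 12.1 plans a blinded review of whether the methods are suitable, and the SAP allows revision before database lock with reasons reported. A cut-point picked after seeing results is therefore a risk, not a certainty. These routes help only if they are used.
- **The item is supportive.** This stands and limits the weight of the point.

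A reader might also infer a definite loss of power against a longitudinal model. The documents do not allow one to be stated. The gain from using more visits depends on when the effect appears, and the concentration rises five-fold every four visits (Appendix H), so the effect could come late. Averaging visits could then dilute it.

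**Conclusion.** The point holds as a misnamed and underspecified supportive analysis. Kaplan-Meier does not fit a continuous score measured at each visit. Neither document supplies what it would need, and the two documents leave the family of method open. This conclusion rests on the text alone and needs no assumption about the data.

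The consequence is confined to item 3 and its counterpart in protocol section 12.1.3. The four primary t tests, including mini-RQLQ change to visits 17 and 18, are untouched, and the sample size does not depend on this item. The spread of 0.18 to 0.56 shows that the missing event definition could matter a good deal; it rests wholly on the assumed inputs and does not estimate this trial's power. The item is worth correcting before unblinding because the correction is cheap, not because the main result is at risk.

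**What to change.** Before unblinding, replace Kaplan-Meier in SAP item 3 and protocol section 12.1.3 with the same single analysis:

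- A mixed model for repeated measures on mini-RQLQ at visits 3 to 18, with treatment, visit, treatment-by-visit and the visit 2 mini-RQLQ as baseline.
- A named, parsimonious covariance, for example a random intercept plus AR(1). The correlation is better indexed by study day than by visit number, since visit 18 comes about a month after the last injection.
- A small-sample degrees-of-freedom correction such as Kenward-Roger.
- A stated missing-at-random assumption.
- The treatment difference with 95% confidence interval at visits 17 and 18 as the named contrasts, matching the time points of the primary comparisons.

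If time to response is really of interest, define the event (size of change, first or sustained), the origin, the censoring rule and the test now, and list it as a separate analysis.

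The cost is a paragraph of SAP wording, a matching edit to the protocol and modest programming. No new data are needed.

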#### **7.1.1 Dosage Form, Preparation and Labeling**

The dosage (dilution) of PMA will be the same for all subjects and will begin with vial number #5 which will be prepared by serial five fold dilutions from the most concentrated vial (#1).

One PMA active treatment set will be prepared by compounding three separate concentrated vials (#1) each containing approximately 30 antigen mixtures (no more than about 75 total antigens each) and labeled mix A, B and C. No more than 0.9 ml of each manufacturer supplied stock material will be placed in a 100ml vial and brought to volume with diluent. Each of the #1 vials (A, B and C) will then be serially diluted 5 fold, several times approximately as follows:

	Mix A (Pollens)	Mix B (Indoor)	Mix C (Molds)	Exact Preparation
Vial #1	1:1	1:1	1:1	Described above
Vial #2	1:5	1:5	1:5	20ml Vial #1 + 85ml diluent
Vial #3	1:25	1:25	1:25	4ml Vial #1 + 85ml diluent
Vial #4	1:125	1:125	1:125	4ml Vial #2 + 85ml diluent
Vial #5	1:625	1:625	1:625	4ml Vial #3 + 85ml diluent

7.1.2 Vials #1-2 will have an expiration date of six months and dilutions #3-5 may be used for up to three months.

7.1.3 One placebo set will also be prepared in a similar manner using sterile saline and an equivalent amount of glycerin/phenol. Because up to 20% of patients receiving active treatment may notice local swelling and itch, histamine will be added to the stock placebo vials (vial 1) at a concentration of 50ug/ml (0.05mg/ml). Thus vial #2 will have a final concentration of 0.01mg/ml histamine. This is expected to elicit a mild itch in about 20% of control subjects based on experience.

Folic acid will also be added to the placebo vials to yield a slightly yellow color similar to the active treatment vials. Stock placebo (#1 vials) will contain 1mg/ml folic acid by adding 20ml of 5mg/ml folic acid to 80ml diluent. This will be further diluted 5 fold to yield (#2 vial) for a final concentration of 0.2mg/ml folic acid and so on.

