#### **Secondary Endpoint**

The secondary endpoints include a symptom score trend analysis, drop out rates, and adverse events profile (AE). Serum will also be stored for measurement of immunoglobulins at a later time.

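### With two arms the Jonckheere-Terpstra test is the Mann-Whitney test, so the only trend test the SAP names tests no trend and the reason given for it does not apply

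*Combined protocol and SAP*

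**What the plan says.** The SAP, Other Comparisons and Outcomes, item 5, proposes "an appropriate test, such as the Jonckheere-Terptsra trend test, based on a sum of Mann-Whitney-Wilcoxon tests". Its justification is that such a test "may be sensitive and reveal a mild trend where pair-wise comparisons may not be able to find significant differences". The item ends by leaving the choice open: "Other trend tests may also be used".

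Protocol section 12.1.3 says what is to be compared: "Trend tests for comparison of both groups will be performed such as the Jonckheere-Terptsra trend test".

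The design has two groups. The SAP, Study Design, states: "Randomization to active PMA versus placebo treatment is on a 1 to 1 ratio". There is one active regimen; protocol section 7.1.1 states: "The dosage (dilution) of PMA will be the same for all subjects and will begin with vial number #5".

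The status of the analysis differs from place to place. The SAP, Secondary Endpoint, reads: "The secondary endpoints include a symptom score trend analysis, drop out rates, and adverse events profile (AE"). The SAP's itemised Secondary Outcomes list TNSS and adverse events and contain no trend analysis. The test appears only under Other Comparisons and Outcomes. The protocol's own secondary endpoints (synopsis, sections 2.1.2 and 4.1.2) do not mention trend.

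The planned between-arm comparison for the scores is a t test on change: "Comparison of the delta visit 2 to visit 17 (change in score) between both treatment groups I and II using an unpaired t test".

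**The concern.** Jonckheere-Terpstra gains power over separate pair-wise tests by pooling evidence across several groups whose order is known in advance, for example rising dose levels. Here there are two arms and one pair, so there is no order to exploit.

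An analyst who follows the SAP as written would therefore report a two-group location test as the trend result. The trend analysis also has no named score, time window, grouping or contrast, and further tests are allowed without limit. In a trial of up to 36 subjects, that leaves room to choose a trend test after seeing the data, under a rationale that speaks of finding what the planned comparisons miss.

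**Working it through.** **Inputs.** Two arms, 1:1 (SAP, Study Design). Up to 36 subjects recruited, hence 18 per arm, and a calculated requirement of 28, hence 14 per arm (protocol section 12.3). The documents state no figure for the trend test, so there is none to reproduce. The sample size rests on response rates and does not enter this check.

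**Step 1: the statistic.** J is the sum of Mann-Whitney U over all pairs of ordered groups. With k groups there are k(k − 1)/2 pairs. With k = 2 there is one, so J = U.

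**Step 2: the null distribution (no ties).**

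- Jonckheere-Terpstra: mean = (N² − Σnᵢ²)/4; variance = [N²(2N + 3) − Σnᵢ²(2nᵢ + 3)]/72.
- Mann-Whitney: mean = n₁n₂/2; variance = n₁n₂(N + 1)/12.

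At 18 versus 18 (N = 36):

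- Jonckheere-Terpstra: mean = (1296 − 648)/4 = 162; variance = (1296 × 75 − 2 × 324 × 39)/72 = (97,200 − 25,272)/72 = 999.
- Mann-Whitney: mean = 324/2 = 162; variance = 324 × 37/12 = 999.

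| Arms | Mean, both tests | Variance, both tests |
|---|---|---|
| 18 vs 18 | 162 | 999 |
| 14 vs 14 | 98 | 473.67 |
| 15 vs 18 | 135 | 765 |

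In 3,000 simulated data sets at 18 versus 18 the largest difference in the statistic was 0 and the largest difference in p-value was 0. With tied integer scores (another 3,000) the statistics again agreed exactly.

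**Step 3: against the planned t test.** The documents give no SD or effect size for the scores, so the standardised difference d is an assumption. Two-sided power at 18 per arm (20,000 simulations):

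| Data | d | t test | Jonckheere-Terpstra = Mann-Whitney |
|---|---|---|---|
| Normal | 0.5 | 30.7% | 29.5% |
| Normal | 0.8 | 64.3% | 62.5% |
| Normal | 1.0 | 83.0% | 81.2% |
| Heavy-tailed (t, 3 df) | 0.8 | 72.7% | 85.7% |

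The rank test is slightly weaker with normal data and stronger with heavy tails. The gain in the last row is the ordinary Mann-Whitney gain and has nothing to do with trend.

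**Step 4: visits as the ordered groups.** Treatment visits run from 2 to 17 (Appendix A), so one subject could contribute 16 scores to groups that the test takes to be independent. The documents give no correlation structure. Under assumed ones, with 16 visits, no true time trend and a nominal 5% level, simulated rejection was about 0–1% for constant within-subject correlation of 0.5–0.7, and about 23–28% for first-order autoregressive correlation of 0.8–0.9. With subject-specific slopes it ran from a few per cent to over 20% as the slope variance rose. The error can fall on either side of 5%. Even with a correct level, the test would address change over time and not active versus placebo.

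**The case against.** Four points can be made for the plan.

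- **The test is only an example, listed under Other.** This is true. A reader might infer that the SAP formally assigns Jonckheere-Terpstra to a secondary endpoint. It does not: the link comes from one overview sentence, and the itemised secondary outcomes do not carry it through. What stands is that no other trend test is named anywhere and that the sections disagree on the status of the analysis.
- **The test is valid with two groups.** Also true. A reader might infer that it cannot be run or would give a wrong p-value. It gives a correct Mann-Whitney p-value; the fault is in calling that a trend result and in the reason given for choosing it.
- **A rank test may detect what the t test misses.** It may, with heavy-tailed scores. A claim of no possible gain over the planned analysis would go too far, because the planned pair-wise test is a t test and not Mann-Whitney. The zero gain is exact only against Mann-Whitney.
- **Visits may have been intended as the groups.** Neither document says so, and section 12.1.3 points to the two arms. A reader might also infer a particular inflation of type I error from this use. The documents do not support any one figure, since both size and direction depend on a correlation structure they do not give.

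**Conclusion.** The point holds. Given two arms and one active regimen, Jonckheere-Terpstra and Mann-Whitney coincide exactly in statistic, null mean, variance and p-value. This needs no assumption about the data. The named test examines no trend, and its claimed advantage over pair-wise comparison cannot arise here.

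The power figures and the visit-based error rates are illustrations under assumed inputs. The conclusion does not depend on them; for the visit reading it is enough that independence fails and that the arms are not compared.

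The consequence is limited to the trend analysis, which is left without an estimand, a fixed method or a settled status. The four primary comparisons are named t tests and stand apart from it, and the sample size is unaffected. The matter should be corrected before unblinding but does not threaten the primary result.

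**What to change.** 1. Delete Jonckheere-Terpstra and the clause allowing other trend tests from SAP item 5, and align protocol section 12.1.3.
2. Decide whether the trend analysis is secondary or other, and make the SAP's Secondary Endpoint, Secondary Outcomes and Other Comparisons sections agree.
3. If it is kept, prespecify one two-sided treatment-by-time contrast from a repeated-measures mixed model, and name the score.
   - Section 12.1.3 has mini-RQLQ recorded at every study visit, so it can support a difference in slope over visits 2 to 17. It is a quality-of-life questionnaire, so the SAP must then say that it replaces the symptom score in the Secondary Endpoint text.
   - If TNSS or DCS is meant, use the daily-card weeks 2, 10 and 14. Appendix A lists TNSS alongside RQLQ at treatment visits, but the visit form in Appendix J has no field for it.
   - A linear slope is a modelling assumption and should be stated as one.
4. Otherwise, drop the trend endpoint.

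**Cost.** No new data or subjects. It is somewhat more than rewording, because neither document contains a mixed model: SAP item 3 of the same list offers only Kaplan-Meier or some comparable repeated-measures method, so the model has to be written.
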